12.3.3.1 Genetic Testing Patient Rights

All patients have the right to refuse genetic testing. Patients who wish to undergo genetic testing, based on family history or otherwise will be required to meet with a genetic counselor, and if they choose, will have genomic DNA testing done at Myriad Genetics.

Moreover, for this study, patient tumor samples which are used to test expression patterns of DNA repair enzymes will be deidentified (as detailed below).

[figure not shown]

Figure 5: Step-wise screening for Patients with Possible Familial Pancreatic Cancer

12.3.4 Defining a novel response signature

RNA samples obtained as described above will be used as a resource to study a, logical focused group of DNA repair pathway genes that have been shown to be good candidate targets (see Table 7). We will use the samples processed above with Super Array technology (SA Biosciences) to screen for a putative molecular signature from their pathway specific array (DNA repair). These platforms are based on straightforward real-

time, optimized PCR technology which includes a web-based program that performs statistical, data analysis. As noted PARP-1 and related genes are all part of this condensed array platform. If other related DNA repair genes emerge in the literature, we will add them to our platform immediately.

Table 7: DNA Repair Enzymes to be Analyzed (SA Biosciences):

Enzyme Class	Specific Gene Abbreviations
Damaged DNA Binding	Brca1, Brca2, FANCC, FANCG, FANCF Ercc1, Ercc2, H2afx, Msh2, Msh3, Rad1, Rad51, RGD1563765 (Rad51c), RGD1564823 (Xrcc2), Rad51l1, Trpc2, Xpa, Xpc, Xrcc1, Rad1, Rad9, RGD1566025 (Pinx1), Smc1l1 (Smc1a), Tp53. Base-excision Repair: LOC680915 (Mbd4), Mpg, Mutyh, Nthl1, Ogg1, Parp1 (Adprt1), Parp2 (Adprt1), RGD1308665 (Mare)
Base-excision Repair	LOC680915 (Mbd4), Mpg, Mutyh, Nthl1, Ogg1, Parp1 (Adprt1), Parp2 (Adprt1), RGD1308665 (Mare).
Nucleotide-excision Repair	Dclre1a, Fancc, Nthl1, Rad23a, Slk, Xpa, Xpc
Double-strand Break Repair	Brca2, H2afx, Mre11a, Prkdc, Rad52, Xrcc6 (G22p1)
Mismatch Repair	MGC72584 (Pms1), Mlh1, Mlh3, Msh2, Msh3, Pms2, Pold3, Trex1
Other Genes Related to DNA Repair	Apex1, Atm, Atrx, Cry2, Cspd6 (Smc3), Exo1, Fen1, Gtf2h1, Gtf2h2, Lig1, LOC363333 (Chaf1a), LOC685491 (Rbbp4), LOC691105 (Fancg), Mgmt, Mif, Pold1, Pole, Polh, Poli, Polk, Pttg1, Rad17, Rad18, MGC116373 (Rad21), Rad50, Rad9, Rad9b, Rbm4, Rev1l, Smc1l1 (Smc1a), Srd5a2, Sumo1, Tdg, Tnp1, Ube2a, Ung, Wrn, Wrnip1, Xrn2, ERCC1, ALD6IP6, SSBP2

12.3.5 Construction of pancreatic cancer tissue arrays obtained from the trial

Central to the successful analysis of such a large number of tumors in a cost-effective manner, is a newly devised tissue arraying approach that is particularly well suited for arraying multiple pancreatic tumors. This arraying technology is based on serial transverse cutting and edge-to-edge-bonding of thick tissue sections to assemble a high density matrix of rectangular tumor specimens, termed cutting edge matrix assembly (CEMA)(24-26). The technology has been developed by our collaborator at Thomas Jefferson, [name], and is simple, fast, and relies on standard equipment available in histotechnology laboratories. Increased sample density is achieved by a self-supporting construction that eliminates space loss due to a structural scaffold (e.g. paraffin block). CEMA uses a space saving rectangular feature design instead of circular features, and includes improved control of sample quality, and availability of thick tumor blocks is not a requirement(25, 27). Each block will be sectioned and stained with H&E for pathologic evaluation of the pancreatic cancer. A 300 μ m thick section is then cut from the face of the block, and is used for construction of the CEMA arrays as described(24-26).

At the completion of the trial we will construct an array of all 50 pancreatic cancer specimens. These specimens will be represented once in each array block with a 2 mm² "tissue spot" (0.3mm x 6.6mm). Five replicate array blocks will be generated to achieve 5 parallel array replicates for 5-fold redundancy, ensuring representative analysis of pancreatic cancer cells in each specimen. The three key benefits of tissue arrays are 1) parallel *in situ* analyses of multiple samples without confounding inter-assay variation, 2) side-by-side quantitative image analyses on samples treated the same way, and 3) extraordinary savings in histology processing and reduced reagent cost due to low incubation volumes needed.

12.3.6 Validation of array platform: *In situ* biomarker profiling and quantitation using the AQUA system

The immunostaining will be performed using our validated antibodies and established conditions published(28, 29). Marker levels discovered in our DNA repair platform analysis (see task 2) in individual pancreatic cancer specimens will be determined by automated quantitative analysis (AQUA) using multiplexed and fluorescence-based immunodetection on the AQUA/ PM2000 platform(30, 31) available in Kimmel Cancer Center Histopathology Translational Research Core (TJU). Pancreatic cancer specimens will be analyzed at 5-fold redundancy for representative and accurate quantification of proposed markers. In total, there will be 4 replicate arrays that will be analyzed for all new promising markers that are identified.

[figure not shown]

Figure 6: DNA Repair Pathway Testing Algorithm

12.3.7 Assessment of ERCC1, RRM 1, and Thymidilate Synthase

A portion of patient tumor samples will be sent to Response Genetics for laser capture microdissection of tumor samples, and assessment by quantitative RT-PCR of levels of expression of genes involved in response to chemotherapeutic agents. These include ERCC1, Thymidilate Synthase, and RRM1. These tests are performed at a Clia certified lab, and are not billed to patients or insurance.

12.4 Protection of Patient Confidentiality

All patient records, questionnaires, and tissue specimens will be de-identified using a letter and number assigned to their case at the time of enrollment on study. No record or specimen will contain information which could identify the patient. The key which connects patient identifiable information with this assigned number will be held by the Principal investigator. For computer records, the key will be protected by a double password protection system. Any paper records will be contained in a locked cabinet within a locked office to ensure patient's privacy is protected.

13.0 STATISTICAL CONSIDERATIONS

13.1 Objectives

The primary objective of the phase I portion of this study is to establish the recommended phase II dose. The primary objective of the phase II study is to determine the objective response rate (CR+PR) of ABT-888 combined with 5FU and oxaliplatin in patients with metastatic pancreatic cancer, stratified by prior therapy. Secondary clinical objectives include determining the disease control rate, progression free survival, overall survival, time to disease progression, duration of disease control, and tolerability and safety of the combination of ABT-888 and 5FU and oxaliplatin.

The secondary scientific objectives include examining the association between response to ABT-888 plus 5FU and oxaliplatin to: 1) Tumors that have decreased expression of or mutations in BRCA-1 or -2; 2) PARP activity levels in serial tumor samples; 3) The expression levels of DNA repair enzymes in tumor tissues; and 4) Pharmacokinetic and pharmacogenomic parameters associated with the metabolism of ABT-888; as well as 5) To isolate and propagate tumor cell lines obtained from patient samples and circulating tumor cells.

13.2 Study Design

The dose of ABT-888 will be determined by a brief Phase I dose escalation study. A traditional 3+3 dose escalation approach with doses of ABT-888 ranging from 40mg to 300mg will be employed to determine the recommended Phase II dose of 5FU and oxaliplatin plus ABT-888. It is possible, even likely that the Phase I portion of this study will identify the RP2D of ABT-888 as 40mg, thus as few as 9 patients may be enrolled in the Phase I portion of the study.

This trial will follow a standard 3+3 Phase I design. Patients are enrolled in groups of three. The following dose escalation rules will be used and applied to Cycle 1 of therapy:

- 1) Three patients are studied at the first dose level.
- 2) If none of these three patients experience DLT, then the dose is escalated to the next higher level in the three subsequent patients.
- 3) If one of three patients experiences DLT at the current dose, then up to three more patients are accrued at the same level.
 - a) If none of these three additional patients experience DLT, then the dose is escalated in subsequent patients.
 - b) If one or more of these three additional patients experiences DLT, then patient entry at that dose level is stopped, the MTD has been exceeded and dose escalation will be stopped. Up to three more patients are treated at the next lower dose (unless six patients have already been treated at that prior dose).
- 4) If two or more of a cohort of up to six patients experience DLT at a given dose level, then the MTD has been exceeded and dose escalation will be stopped. Up to three more patients are treated at the next lower dose (unless six patients have already been treated at that prior dose).
- 5) Using this dose escalation scheme, the probability of escalating to the next dose level, based on the true rate of DLT at the current dose, is given by the following table:

True DLT rate at a Given Dose						
	10%	20%	30%	40%	50%	60%
Probability of Escalating	.91	.71	.49	.31	.17	.08

Thus, if the true underlying proportion of toxic events is 30% at the current dose, there is a 49% chance of escalating to the next dose.

The phase II portion of the trial will follow two parallel Simon's two-stage optimal designs(1) that will continue or stop independently from one another. For each stratum, in the first stage, 9 patients will be accrued. If none

of the 9 patients achieve an objective response with ABT-888 plus 5FU and oxaliplatin, the combination will be rejected and the trial stopped. However, if at least 1 patient of the 9 (11%) exhibits response in the first stage, then an additional 15 patients will be entered into the second stage, for a total of 24 patients in this phase II study. If 3 (12%) or more patients exhibit response, then the treatment will be considered for further investigation. *Because of the change in the inclusion criteria prior to initiating Phase II, patients enrolled in the Phase I portion of the study at the phase II dose will not be included in the efficacy assessment as part of the Simon Two Stage design.*

13.3 Sample Size Considerations

For phase I, the sample size will range from 3 to 48 (estimate =24) depending on DLTs experienced. For each stratum of the phase II portion, the sample sizes of 9 and 24 patients and the decision rules, in stages 1 and 2 respectively, are designed to differentiate a 25% ORR from a 5% ORR. The ORR associated with single agent gemcitabine (the standard of care in pancreatic cancer) is only 8% across multiple large Phase III trials. The ORR of the combination of 5FU and oxaliplatin in the first or second-line setting ranges from 2.5 to 23% in Phase II studies. Thus the lower efficacy limit of 5% is essentially that of gemcitabine, and would suggest the combination is no more effective than single agent gemcitabine, and further investigation would not be warranted. The upper efficacy limit of 25% would be the highest observed to date in a Phase II study of 5FU and oxaliplatin in pancreatic cancer, and would be highly suggestive of a significant benefit to the addition of ABT-888 to the regimen and there would be sufficient evidence to warrant further investigation of this combination. The probability of erroneously concluding that the treatment regimen merits further investigation is 10% ($\alpha=0.10$) when the true ORR is less than 5%. Similarly, the probability of erroneously concluding that the treatment has an ORR of 5% (p_0) or less when the true ORR is 25% (p_1) is 10% (β); therefore the overall power of the study is 90%. The decision rule for this Simon design will accept this agent for further investigation if the sample ORR is 12% or greater at the end of stage 2.

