This stratified trial will follow two Simon's two-stage optimal designs(1), one for the untreated group, and one for the previously treated group. Each study (or otherwise stated, each stratum) has the same hypothesized design which will run in parallel. For the first stage, 9 patients will be accrued. If none of the 9 patients achieve a partial or complete response with ABT-888 plus 5FU and oxaliplatin, the combination will be rejected and the trial stopped. However, if at least 1 patient of the 9 (11%) achieves a partial or complete response in the first stage, then an additional 15 patients will be entered into the second stage, for a total of 24 patients in each stratum of these Phase II studies. If 3 (12%) or more patients achieve a partial or complete response, then the combination will be considered for further investigation among those patients. The sample sizes of 9 and 24 patients and the decision rules, in stages 1 and 2 respectively, are designed to differentiate a 5% ORR from a 25% ORR at a 1-sided 10% significance level and 90% power. Historically, the response rate of patients receiving single agent gemcitabine (previously considered the standard of care) is only about 8%.

[figure not shown]

Figure 1: Treatment schema

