5.2 Targeted therapies against DNA repair in pancreatic cancer

One of the defining hallmarks of gastrointestinal malignancies including pancreatic cancer is chromosomal instability (CIN). The critical events that contribute to CIN, and thus pancreatic tumorigenesis, are linked to a disruption in an internal repair system that can set the stage for DNA mutations and events such as loss of heterozygosity (LOH) of tumor suppressor genes. Furthermore, the ability of pancreatic cancer cells to thrive with such genetic instability provides an opportunity to target an altered DNA repair network in pancreatic cancer cells. Logically, it has been shown that a defect in this repair pathway can render pancreatic cancer cells hypersensitive to DNA damaging agents. This approach has shown success in pre-clinical models. For instance, pancreatic cancer cells altered in the DNA repair genes, *BRCA2*, *FANCC* and *G* (labeled as "BRCA-deficient"), are all hypersensitive to intra-strand cross-linking agents and platinum-based drugs in *in vitro* and *in vivo* models(8). It has been estimated that roughly between 5-10% of sporadic pancreatic tumors, and over 15% of familial cases harbor mutations in this BRCA-pathway, including the recent discovery of *PALB2* mutations(9). Regardless of whether mutations were artificially introduced or naturally occurring in pancreatic cancer cells(8), all pre-clinical models selected platinum drugs as promising therapeutic choices to target pancreatic tumor cells deficient in this repair pathway. Additionally, Ashworth and colleagues showed that cells deficient in the homologous recombination repair pathway of double-stranded breaks (including *RAD51*, *RAD54*, *DSS1*, *RPA1*, *NBS1*, *ATR*, *ATM*, *CHK1*, *CHK2*, *FANCD2*, *FANCA*, or *FANCC*) are also hypersensitive to a promising new class of drug, PARP-inhibitors(10, 11). Specifically, it has been shown that cells that are deficient in *BRCA2* and related genes are sensitive to PARP inhibitors(10). Hence, PARP inhibitors are being investigated as a therapeutic option for various cancers disrupted in the *BRCA2* pathway. Conceptually, tumors with loss of expression due to a 'second hit' of the DNA repair gene will be more sensitive to these targeted agents than normal cells, thus providing a good therapeutic window(8, 12). It also has been shown that increased or aberrant PARP expression in cancer cells is a mechanism of chemo-resistance(13). Accordingly, PARP-inhibitors have shown success in sensitizing cells to platinum based therapy(14). This suggests that PARP-inhibitors can effectively sensitize both BRCA-proficient and deficient pancreatic cancer cells to agents such as oxaliplatin. This strategy is borrowed loosely from the concept of targeting cancer cells from two points of the same pathway (i.e. synthetic lethality), which may break the *de novo* and acquired chemo-resistance inherent to most pancreatic cancer cells. Thus, this strategy may work for the majority of pancreatic cancers ("BRCA-proficient") and may be especially beneficial for a subset of patients with BRCA-deficiency in their tumor cells.

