Furthermore, it has been demonstrated in a BRCA-2-deficient breast cancer xenograft model that ABT-888 also significantly increases the antitumor efficacy of cisplatin and carboplatin (Figure 4)(14). Given the known sensitivity of BRCA2-deficient pancreatic cancer cells to oxaliplatin, and the enhanced effects of ABT-888, as shown in figure 2, the addition of ABT-888 to platinum-based therapies (mFOLFOX-6) may optimize an already promising treatment strategy against tumors with BRCA-deficiency. Thus, the combination of ABT-888 and a platinum analog is effective in both BRCA-proficient and -deficient tumors(10), laying the proof-of-principle work that ABT-888 can sensitize pancreatic cancer cells (regardless of a defined genetic alteration in a DNA repair gene) to a platinum based drug (*i.e.*, oxaliplatin). Moreover, targeting two aspects of the repair pathway follows the logic of inducing synthetic lethality in cancer cells, and not allowing cancer cells the opportunity to develop *de nova* drug resistance (*i.e.*, an acquired addiction to other aspects of the repair network).

[figure not shown]

Figure 4. In a BRCA-deficient breast xenograft model ABT-888 increased the sensitivity of these tumors to cisplatin and carboplatin (as shown here)(14). A dose increase in ABT-888 enhances the therapeutic reduction of tumor volume in mice.

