8.2 Selection of Study Population

This is a multi-institutional study for patients with metastatic pancreatic cancer. Only patients with metastatic pancreatic cancer not amenable for resection will be considered for entry. Subjects must have measurable disease, defined as at least 1 unidimensionally measurable lesion on a CT scan as defined by RECIST.

The target recruitment for this study is 24+48 patients. At the LCCC alone, approximately 150 new cases of pancreatic cancer are seen yearly, at least one-third of which have metastatic disease. Because patients with both untreated (for metastatic disease) and pretreated cancers are eligible, most patients seen in the medical oncology clinic with metastatic disease will be eligible for this trial. As of April 2013, the enrollment criteria were modified to include only patients with a known BRCA-associate genetic mutation OR family history suggestive of a breast or ovarian cancer syndrome (as defined below), which is likely to delay enrollment. However, concurrently, the trial is opening at several centers, which may compensate for the

slower accrual. Therefore, recruitment is anticipated to take 24 – 30 months, and with each patient followed for a minimum of 8 weeks, the anticipated time to complete follow-up of all patients will be 30 – 36 months.

Subjects will undergo screening procedures within 14 days prior to administration of the first dose of ABT-888 on Day 1, unless otherwise specified (though baseline imaging scans must be done within 28 days of Day 1). Adult male and female subjects who meet all the inclusion criteria and who do not meet any of the exclusion criteria will be eligible for enrollment into the study.

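### The 5% and 25% design rates come from benchmarks with no described genetic selection, while Phase II enrols only BRCA-mutation or family-history patients; passing the rule, or a 25% ORR, therefore does not show that ABT-888 adds benefit

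*Combined protocol and SAP*

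**What the plan says.** Each Phase II stratum (untreated, previously treated) follows the same Simon two-stage rule: stop at 0 responses in 9, otherwise enrol 15 more and pass at 3 or more of 24. The synopsis (2.5) describes it as "designed to differentiate a 5% ORR from a 25% ORR at a 1-sided 10% significance level and 90% power".

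Section 13.3 gives the source of the rates. The lower limit of 5% is presented as essentially the gemcitabine rate, quoted there as 8%. For the backbone, "The ORR of the combination of 5FU and oxaliplatin in the first or second-line setting ranges from 2.5 to 23% in Phase II studies". The upper limit of 25% is described as the highest yet seen with 5FU and oxaliplatin, and the section treats it as strong evidence that adding ABT-888 helps. Section 13.3 attaches the 10% error to a true ORR below 5%.

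Section 8.2 records a change dated April 2013, by which "the enrollment criteria were modified to include only patients with a known BRCA-associate genetic mutation OR family history suggestive of a breast or ovarian cancer" (the sentence goes on to call this a syndrome, and 8.2.1 gives the criteria). Section 13.2 draws one design consequence, in a sentence that opens "Because of the change in the inclusion criteria prior to initiating Phase II, patients enrolled in the Phase I portion of the study at the" and goes on to leave those treated at the dose chosen for Phase II out of the Simon efficacy count. The rates, sample sizes and cut-offs are not re-justified for the new population.

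On biology, 5.2 says that pancreatic cancer cells altered in BRCA2, FANCC or FANCG "are all hypersensitive to intra-strand cross-linking agents and platinum-based drugs in" pre-clinical models. Section 5.4.1 begins an argument with "Given the known sensitivity of BRCA2-deficient pancreatic cancer cells to oxaliplatin". Sections 2.6 and 12.0 add, tentatively, that repair deficiency may predict a higher ORR.

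**The concern.** Oxaliplatin is part of the backbone that every patient receives. If eligibility favours tumours that respond to platinum, responses can rise with no contribution from ABT-888. The design rates were set without that selection in view. Section 13.2 treats the eligibility change as important enough to set the Phase I patients aside, yet 13.3 carries the benchmarks over unchanged.

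What is at stake is how a pass is read. With one arm and no carrier-specific benchmark, 3 responses in 24 could come from the backbone acting in a selected population. Section 13.3 nevertheless ties the upper rate to a benefit of ABT-888. Under 2.5, a pass means "then the combination will be considered for further investigation among those patients", that is, for the whole stratum. Section 8.2.1 places in one stratum documented carriers, patients with an indeterminate variant, patients whose relative has a mutation, and patients who qualify on history alone.

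**Working it through.** **Inputs.** From 2.5, 13.2 and 13.3: n1 = 9, stop at 0; n = 24, pass at 3 or more; p0 = 5%, p1 = 25%. Benchmarks: 8% for gemcitabine (13.3); 2.5 to 23% for 5FU + oxaliplatin (13.3); 10% and 27% in two first-line trials of that combination (5.6). Mutation share: 5-10% of sporadic tumours and over 15% of familial cases (5.2). The ORR of 5FU + oxaliplatin in BRCA-mutation or family-history patients is not given, so it is an assumption below.

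**Formula.** With true ORR p, the chance of passing in one stratum is

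P(go) = Σ over x = 1 to 9 of Pr[Bin(9, p) = x] × Pr[Bin(15, p) ≥ 3 − x].

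**Reproducing the plan.** At p = 0.05:
- one response in stage 1: 0.29854 × 0.17095 = 0.05104
- two responses: 0.06285 × 0.53671 = 0.03373
- three or more: 0.00836
- sum: 0.0931

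At p = 0.25 the same formula gives 0.9028. A search over designs with error at most 10% and power at least 90% returns this rule as the Simon optimal design. The plan's figures are correct on their own terms.

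**The same rule at other true ORRs.**

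| True ORR without ABT-888 benefit | P(go) per stratum |
|---|---|
| 5% | 9.3% |
| 8% (gemcitabine figure) | 24.7% |
| 10% (a first-line figure in 5.6) | 36.4% |
| 15% | 62.9% |
| 20% | 80.5% |
| 23% (top of the range in 13.3) | 87.1% |
| 25% | 90.3% |

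P(go) crosses 10% at a true ORR of about 5.2% and 20% at about 7.2%, so a small shift in background rate matters.

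**The 25% figure.** Section 13.3 itself sets 25% by reference to 5FU + oxaliplatin, and 5.6 reports 27% for a first-line trial of that combination. By the plan's own account, rates of this order have been seen without ABT-888.

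**Illustration of selection.** Assume 15% carriers (borrowed from the familial figure in 5.2), non-carriers at 5%, and carrier ORR r. All three are assumptions. The pooled ORR is 0.15r + 0.85 × 0.05.

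| Carrier ORR r | Pooled ORR | P(go) |
|---|---|---|
| 10% | 5.75% | 12.7% |
| 15% | 6.5% | 16.4% |
| 20% | 7.25% | 20.5% |
| 30% | 8.75% | 29.1% |
| 40% | 10.25% | 37.9% |

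The range is about 13% to 38%, with ABT-888 adding nothing.

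**The case against.** **The 10% is conditional.** It applies to a true ORR below 5%, and there it is right in any population. The 5% is also framed as a level of no interest for the regimen, not as the backbone's rate, so advancing a regimen with a true 15% ORR is not a type I error under that null. This stands. What does not carry over is 5% as the rate expected when ABT-888 does nothing.

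**The hypersensitivity is pre-clinical and partial.** A reader might infer that the protocol calls the enrolled patients' tumours platinum-hypersensitive. It does not: 5.2 and 5.4.1 speak of BRCA-deficient cells, and eligibility also admits patients with no documented mutation. The direction is supported; the size is unknown.

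**Selection is not the whole cause.** The 5% is already below the 8% that it is said to match, and the rule passes 24.7% of the time at 8%. The general benchmarks also contain some carriers. With non-carriers at 5% and carrier ORR of 20% to 40%, P(go) is 16% to 28% at 10% carriers and 20% to 38% at 15%, a difference of about 4 to 10 points. This stands too. Correcting the lower rate to 8% would still leave a benchmark with no described genetic selection.

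**An analysis by BRCA status is planned.** Section 13.5.2.1 compares ORR by decreased expression of, or mutation in, BRCA-1 or -2. It specifies no interval and no split by stratum. It also does not cover PALB2 or the FANC genes, which 8.2.1 accepts for entry. It helps but does not settle how a pooled pass should be read.

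**Any single-arm trial has this limit.** True, and it is why 13.3 should not attribute the result to ABT-888.

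**Conclusion.** The point holds in limited form. The benchmarks in 13.3 are not described as genetically selected, Phase II is selected, and the rates were not revisited. The design arithmetic is sound: 9.3% at 5% and 90.3% at 25%. If the ORR without ABT-888 is 8% to 20% in the enrolled patients, a stratum passes 24.7% to 80.5% of the time with no ABT-888 effect. A pass, or an ORR of 25%, can show activity of the three-drug regimen but not benefit from ABT-888.

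Two stronger readings are not supported. One is that the stated 10% error is simply wrong: it is correct under its own condition. The other is that the eligibility change at least doubles the error. That depends on assuming a carrier ORR of 20% or more; at 10%, with 15% carriers, P(go) is 12.7%. The conclusion rests on the direction of the protocol's own biological argument. The size rests on assumed carrier shares and carrier ORRs, because the documents give neither for this population.

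**What to change.** Keep the sample size and the decision rule.

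1. **Section 13.3.** State that the benchmarks come from patients not selected genetically, and that the 10% error holds only if the ORR in the selected population is about 5% or less. Give P(go) at 8%, 10%, 15% and 20% (24.7%, 36.4%, 62.9%, 80.5%). Replace the sentence that reads 25% as strong evidence for adding ABT-888 with one saying that it would show activity of the three-drug regimen in a BRCA/family-history-selected population.

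2. **Section 13.5.2.1.** Within each stratum, also report ORR with exact intervals by mutation status recorded at registration: documented deleterious mutation in the patient; tested without one, including an indeterminate variant; not tested, whether entered on a relative's mutation or on history alone. The untested group is needed because 12.3.3.1 lets patients refuse testing. Present this as descriptive guidance for interpreting a pass, not as a new decision rule. A rule of advancing any group with a response would not control error: 20 patients at 5% ORR show at least one response with probability 1 − 0.95^20 = 64%.

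**Cost.** Wording changes and one table per stratum. The registration form in Appendix 2 already asks for the genetic test summary and the mutation or family-history basis. No patients or procedures are added. The stated claim becomes less favourable and the subgroup intervals will be wide. For example, 15% of 24 is about 4 carriers, and 1 response in 4 has an exact 95% interval of 0.6% (1 − 0.975^(1/4)) to 81% (the p solving (1 − p)^4 + 4p(1 − p)^3 = 0.025).
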